for 5 breaths. Specifically, at the patient's peak inspiration (as seen on the capnography), the study member will start the stopwatch and proceed to hit the 'lap' button for the next 5 consecutive inspiration peaks. These data intervals will be recorded on the data sheet after the 5 breaths are over, as the intervals are conveniently stored and numbered below the stopwatch in the app. We will do this to establish an average baseline respiratory rate for each individual patient. Next, patients who are randomized to Group A will receive three drops of povidone-iodine ophthalmic solution in each eye, with the right eye to receive the drops first. Group B will receive three drops in each eye of ophthalmic balanced salt solution. Similarly, the right eye will receive the drops first; the reason being that we know that there are differences in sympathetic stimulation on the right side of the face vs left (e.g. termination of supraventricular tachycardia) and although we don't know if this effects OCR, we chose to standardize right eye first. The eye drops will be administered by the study anesthesiologist. After application of either solution to the eyes of the patient, any change in ventilation can be detected and timed by observation of the capnography (end-tidal carbon dioxide) and direct observation of the chest wall with use of the iPhone stopwatch feature again. The capnograph is a standard monitor of respiration used during the administration of general anesthesia. Data collected at this time will include whether or not there was a change in respiration, what this change in respiration was, if assisted ventilation was required, how long assisted ventilation was required (if applicable), HR, BP, RR, SaO_2 , ETCO_2 , InspSevo, and ExpSevo. This study intervention and data collection will take less than 5 minutes and the surgical team will then progress with the case as they normally would.

Other data to be collected is as follows:

- Attending anesthesiologist and CRNA
- Age
- Weight
- Sex
- Co-existing diseases
- If the patient was a pre-term birth and if yes, the estimated gestational age at birth
- If premedication was given and if yes, what medication and dose
- If N_2O was used during inhalational induction

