12.0 Data Management

Descriptive statistics by treatment group will be evaluated for all demographic and procedural characteristics. The goal of the study is to determine if there is a significant difference in the change in respiratory response immediately following administration of saline or povidone-iodine solution in patients undergoing strabismus surgery. The primary outcome is the difference between the peak to peak interval time from the capnograph measured before saline or povidone-iodine administration versus after administration. Pre-exposure peak to peak interval will be measured as the average time between peaks for five breaths prior to administration. Post-exposure peak to peak interval will only be evaluated as the time between the two peaks at saline or povidone-iodine administration. Differences in the change in peak to peak interval time between the saline and povidone-iodine exposure groups will be evaluated using a linear regression approach. The model will include a treatment effect and will additionally control for patient age, history of prematurity, and use of any pre-medication to account for other factors thought to be associated with respiratory rate. We anticipate no change in peak to peak interval time in the saline group with variability of ± 4 seconds. A sample size of 50 patients per treatment group (100 patients total) provides $>80\%$ power to detect an increase in change in peak to peak interval of 2.5 seconds in the povidone-iodine group compared to the saline group assuming equal variance between the two groups using a 2-sided test with significance level set at alpha = 0.05. If the variability of the povidone-iodine group is larger, for example a variability of 8 seconds, compared to 4 seconds in the saline groups we still have 80% power to detect an increase in the povidone-iodine group of approximately 4 seconds.

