15.0 Risks to Subjects

The risks to the subjects are minimal. The anesthetics will be standard of care and the BSS and povidone-iodine ophthalmic solutions are commonly used eye surgery solutions that are safe for the application to the ocular surface in the manner in which we propose, as deemed by the FDA. These solutions are routinely used during strabismus surgery. As stated previously, the duration of the study intervention is very brief (seconds, to 4 minutes) and will cause minimal, if any, delay in the surgical procedure. If apnea becomes significant (e.g. arterial oxygenation saturation less than 94%, as measured by pulse oximetry), assisted or controlled ventilation is very easily provided via the LMA to counteract the apnea.

There is a risk of loss of confidentiality, but the anesthesia research team has safeguards in place for keeping patient health information secure and only accessed when absolutely necessary. All data will be stored on a secure server and consent and data forms will be held in a locked cabinet in a locked research office.

Though it is a randomized study, there is not a risk of randomization because neither of the possible groups poses any additional risk to the participants.

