Title: *The Effect of Povidone-iodine Ophthalmic Surgical Prep Solution on Respiration in Children Undergoing Strabismus Surgery with General Anesthesia*

NCT03349515

2018 August 15

Statistical Analysis: An *a priori* size calculation was conducted prior to the study. Assuming no change in the peak to peak end-tidal CO₂ interval time after drop instillation in the saline group, and a peak to peak interval time variability of ± 4 seconds, a sample size of 50 patients per group (100 patients total) provided $> 80\%$ power to detect an increase in change in peak to peak interval of 2.5 seconds in the povidone-iodine group compared to the saline group assuming equal variance between the two groups using a 2-sided test with significance level at $\alpha=0.05$.

Descriptive statistics by treatment group were estimated for patient and procedural characteristics. Differences in peak to peak interval time between the saline and povidone-iodine exposure groups were examined using a linear mixed model approach. Based on the *a priori* analysis plan, the model included fixed effects for treatment, breath number, a treatment by breath number interaction and a random subject effect to account for correlation between measures collected on the same subject. The model also controlled for factors thought to be associated with respiratory rate including age, pre-term birth, history of apnea, and breath duration prior to drop installation. Comparisons in breath duration between treatment groups at each of 15 breaths post-drop instillation were estimated from the model using Bonferroni corrected significance.

A secondary outcome of interest was occurrence of a significant change in respiration. Although apnea has been defined in the literature as a breath duration of 10 to 20 seconds, this definition is arbitrary and fails to account for within and between subject variability of breath duration. To account for within and between subject variability, we defined changes in respiration as having a breath duration greater than twice the inner-quartile range above the

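### Section 12.0 rests the primary outcome on one interval with no defined index drop, and the SAP's 15 Bonferroni-corrected comparisons reuse a power figure calculated for a single test

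*Protocol*

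**What the plan says.** Protocol Section 12.0 defines the outcome as a change: "The primary outcome is the difference between the peak to peak interval time from the capnograph measured before saline or povidone-iodine administration versus after administration". The two halves are measured differently. Before the drops, "Pre-exposure peak to peak interval will be measured as the average time between peaks for five breaths prior to administration". After them, "Post-exposure peak to peak interval will only be evaluated as the time between the two peaks at saline or povidone-iodine administration". The arms are then compared by linear regression, with one treatment effect at two-sided 0.05.

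Section 10.0 describes the exposure. Group A receives "three drops of povidone-iodine ophthalmic solution in each eye, with the right eye to receive the drops first"; Group B receives balanced salt solution in the same way. That is six drops, one eye after the other. On timing, Section 10.0 says only that "This study intervention and data collection will take less than 5 minutes", and Section 15.0 gives a range from seconds to 4 minutes. Section 10.0 also has the observer note any change in respiration after the drops, but Section 12.0 does not bring that into the primary outcome. Section 4.0 words the primary endpoint more broadly, as the presence of any respiratory effect, specifically a change in rate.

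The SAP analyses breath duration in a mixed model with treatment, breath number and their interaction, adjusted for pre-drop breath duration and other factors: "Comparisons in breath duration between treatment groups at each of 15 breaths post-drop instillation were estimated from the model using Bonferroni corrected significance". It repeats the protocol's sample-size statement unchanged. Its secondary outcome classifies each child as having a change in respiration or not, using 10 breaths before and 15 after the drops.

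**The concern.** Two things do not fit together.

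First, the protocol's rule allows one post-exposure interval, but the exposure is a sequence. Neither document ties administration to a particular drop or eye, or says that all six drops fall within one breath. Two observers could record different primary values for the same child. Whichever interval is chosen, a pause that begins on a later breath is excluded. If children pause on different breaths, the mean difference at any one breath is diluted.

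Second, the SAP covers later breaths by making 15 comparisons, each at a corrected level, and names none of them as the primary result. Its power statement belongs to a different analysis: one comparison at 0.05. The SAP also does not say which drop starts its count, so a pause during dosing may still fall outside the window.

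What is at stake is the definition of the trial's primary result and whether the stated power applies to it.

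**Working it through.** **Inputs.** Difference 2.5 s, SD 4 s in both arms, 50 per arm, two-sided 0.05 (Section 12.0, repeated in the SAP). Fifteen post-drop comparisons with Bonferroni correction (SAP).

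**Step 1: reproduce the plan's figure.** Standard error = 4 × √(2/50) = 0.8 s. Noncentrality = 2.5/0.8 = 3.125 on 98 degrees of freedom. At 0.05 the critical value is 1.984 and power is 87.2% (87.8% by the normal approximation). The statement of more than 80% is correct for one test in which the full 2.5 s appears in the measured interval.

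**Step 2: the same difference at one breath of the SAP's analysis.** The level is 0.05/15 = 0.0033 and the critical value 3.009. Power is 54.8% (57.5% by the normal approximation). Reaching 80% would need about 74 per arm (normal approximation) or a difference of 3.09 s. This treats one breath as a simple two-sample test and ignores any gain from covariates or the mixed model.

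**Step 3: dilution in the single interval.** Assume a fraction q of the 2.5 s mean effect falls in the measured interval, with SD still 4 s. The documents do not give q.

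| q | Mean difference captured | Power at 0.05 |
|---|---|---|
| 1 | 2.5 s | 87.2% |
| 0.9 | 2.25 s | 79.5% |
| 0.75 | 1.875 s | 64.1% |
| 0.5 | 1.25 s | 34.0% |
| 0.25 | 0.625 s | 12.1% |

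**Step 4: how many intervals dosing could span.** Assume 12 to 30 breaths per minute (not in the documents), so an interval lasts 60/12 = 5 s to 60/30 = 2 s. Thirty seconds of dosing would then span 6 to 15 intervals. Dosing completed within a few seconds could fall inside one.

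**Step 5: single interval against longest of 15, by simulation.** Assumptions: 25% of povidone-iodine children have one pause, exponential with mean 10 s (mean effect 0.25 × 10 = 2.5 s); 50 per arm; Welch test on the value minus baseline.

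- Breath-to-breath SD 0.5 s: the single interval has about 94%, 45%, 20% and 7% power when pauses are spread over 1, 2, 3 and 5 breaths. The longest of 15 keeps about 91–92%.
- SD 2 s: the longest of 15 has about 62–67%. The single interval has about 77% if every pause falls on that breath.
- SD 4 s: the longest of 15 has about 28%. The single interval has about 46% if every pause falls on that breath.
- At SD 2 s and 4 s the longest interval is still well ahead once pauses spread over three or more breaths.

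**Step 6: does the window length matter?** With no treatment effect, SD 0.5 s and 15 breaths in both arms, the longest interval has type I error near 5%. If the window runs from the first drop to a set number of breaths after the last, its length depends on dosing time. Five extra breaths in one arm raise type I error to about 15%, and ten to about 36–38%. The number of breaths must therefore be fixed.

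**The case against.** The best defence is that the SAP already looks beyond one breath. It models 15 post-drop breaths, adjusts for pre-drop duration and includes the treatment-by-breath interaction. That is right, and it closes most of the later-breath gap. Under an approximation to that model with variance pooled over breaths, the chance of at least one significant breath was about 85% when pauses were spread over 5 breaths, 60% over 10 and 45% over 15. So 55% understates the SAP's analysis when pauses cluster early. The pooling assumes equal variance across breaths and arms, though, which pauses in one arm would violate.

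Some stronger readings are tempting but not supported:

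- A reader might infer that the primary outcome is bound to miss the response to one eye. The time between drops is not given, and drops given within one breath would share an interval. What is established is that the index interval is undefined and that later breaths are excluded.
- A reader might infer that no measure captures a pause wherever it falls. The SAP's secondary yes/no outcome does so for each child. The gap is in the primary outcome.
- A reader might infer that the trial's real power is 55% or 34%. Those figures rest on a simplified test or an assumed fraction.

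It can also be said that Section 12.0 aims at the response immediately after administration, so an early window is partly deliberate. That stands as intent, but it does not identify the drop.

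**Conclusion.** The point holds for the primary outcome. Section 12.0 fixes on a single interval without an index drop, and excludes a pause on a later breath on any reading. The SAP widens the window but replaces one test with 15, and carries over a power statement that does not describe them: 87% for one test at 0.05, against about 55% for one breath at 0.05/15 on the plan's own inputs. The protocol and SAP therefore give different primary analyses, and the stated power belongs only to the protocol's.

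The mismatch in level and number of tests follows directly from the documents. The dilution figures and the comparison with the longest interval are illustrative, because the documents give neither the timing of pauses nor the breath-to-breath SD; the planned 4 s is not broken down in that way.

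**What to change.** In Section 12.0 and the SAP:

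1. Name the index drop from which breaths are counted. Counting from the last drop leaves out pauses during dosing; counting a fixed number from the first may leave few breaths after the second eye. State the choice.
2. Define one primary value per child over a fixed number of breaths, the same in both arms: for example, the longest of the 15 post-drop intervals the SAP already analyses.
3. Compare the arms once at two-sided 0.05 by linear regression, adjusted for the mean pre-drop interval and the planned covariates. The protocol and SAP covariate lists differ, so name one.
4. Report the mean interval over the same window as supportive and the 15 per-breath contrasts as descriptive.
5. Restate power for the analysis actually used, with the breath-to-breath SD it assumes.
6. Bring Section 4.0 into line with the chosen value.
7. If data have already been seen, label the new measure post hoc and also report the protocol's single-interval analysis. The SAP states a result for the saline group, so this condition appears to be met.

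The cost is mainly wording. Section 10.0 does not specify recording 15 post-drop intervals, so it needs a matching sentence. There are two statistical downsides. The longest interval does not detect faster breathing, which has to be read from the supportive mean. It also loses some power to the single interval if every pause falls on the first breath.

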14.0 Withdrawal of Subjects (if applicable)

Subjects will be withdrawn from the study if any changes need to be made to the anesthesia plan that do not align with the inclusion/ exclusion criteria of the study; e.g. if any airway intervention other than an LMA is required at the start of surgery.

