3.0 Intervention to be studied

The effect of the application of povidone-iodine ophthalmic solution on the ocular surface on respiration will be compared to the effect on respiration of the application of the application of ophthalmic BSS on the ocular surface during general anesthesia. Both of these solutions are FDA approved for use in this manner and this intervention will begin once a steady state of anesthesia is achieved by means of the standard of care. After the

induction of general anesthesia and at the time the patient is ready for surgical preparation of the eyes, subjects will first have their average peak to peak interval for respiration measured at a steady state of anesthesia, using capnography. This will give us a baseline for measuring a change in respiratory rate. They will then have one of two solutions applied to the ocular surface of each eye. It is this application of eye solution that is the main study intervention. The solution to be used is determined by randomization upon enrollment and will either be 3 drops of povidone-iodine ophthalmic solution in each eye (Group A) or 3 drops of BSS in each eye (Group B). The eye solution intervention period will take less than 5 minutes and will cause either only a slight delay or no delay in the surgical time. The only other intervention is the collection of data after induction (but just prior to IV insertion), as well as before and after the drops of eye solution are delivered.

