5.0 Inclusion and Exclusion Criteria/ Study Population

Operating room schedules will be screened the day prior to surgery and eligible candidates (their families) will be invited to participate in the study on the morning of surgery in the preoperative holding area. The primary reason for including children is that strabismus is normally corrected during childhood and strabismus surgery is of importance because, as was mentioned previously, the oculo cardiac reflex has been known to occur with strabismus surgery.

Inclusion Criteria

- *Children 17 years and less*
- *Scheduled for strabismus surgery*
- *Anesthesia plan includes inhalational induction with sevoflurane and the use of a laryngeal mask airway (LMA) with spontaneous ventilation, per the attending anesthesiologist.*

Exclusion Criteria

- *History of an adverse reaction to iodine*
- *History of any thyroid disease*
- *Patients who require tracheal intubation, as determined by the attending anesthesiologist; e.g. craniofacial anomalies.*
- *Patients with a contraindication to sevoflurane, such as malignant hyperthermia or severe left ventricular dysfunction.*
- *Inability or unwillingness of the subject or legal guardian/ representative to give informed consent.*

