6.0 Number of Subjects

We will enroll approximately 110 patients in this study to include 55 patients for each randomized ‘treatment’ group. Please refer to section 12.0 for the justification behind this enrollment number.

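### Does the withdrawal rule in section 14.0 let a child be dropped from the analysis because of a respiratory response to the drops?

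*Protocol*

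**What the plan says.** **Withdrawal.** Protocol section 14.0 says "Subjects will be withdrawn from the study if any changes need to be made to the anesthesia plan that do not align" with the inclusion and exclusion criteria. Its one example is "if any airway intervention other than an LMA is required at the start of surgery". It sets no time limit and does not say what happens to data already recorded.

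**Eligibility.** Section 5.0 requires an anesthesia plan that includes "the use of a laryngeal mask airway (LMA) with spontaneous ventilation, per the attending anesthesiologist". It excludes children who need tracheal intubation.

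**Sequence.** Under section 10.0 the child is randomized before going to the operating room. The drops follow once the airway is secured and anesthesia is steady. Section 3.0 places them "at the time the patient is ready for surgical preparation of the eyes". After the drops and the data collection, section 10.0 says "the surgical team will then progress with the case as they normally would".

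**Respiratory events after the drops.** Section 10.0 lists among the data to be collected "if assisted ventilation was required, how long assisted ventilation was required (if applicable"). Section 15.0 expects that, if apnea becomes significant, "assisted or controlled ventilation is very easily provided via the LMA to counteract the apnea".

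**Numbers.** Section 6.0: "We will enroll approximately 110 patients in this study to include 55 patients for each randomized" group. Section 12.0 bases power on 50 per group.

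**Analysis set.** Neither section 12.0 nor the SAP defines one.

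**The concern.** The surgical team proceeds only after the drops, so an event at the start of surgery can, read literally, come after them. A child whose response to the drops led to another airway would then meet the example. A strict reader might also treat assisted breathing as a departure from the spontaneous ventilation named in section 5.0.

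Either way, the reason for leaving the study would be the outcome under study. Excluding children after randomization because of their outcome can make the groups no longer comparable. Losing a povidone-iodine responder shrinks the estimated difference, and losing a saline responder enlarges it. The five extra children per group could replace the lost numbers but would not correct a selected estimate.

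**Working it through.** **1. The plan's own power figure.** Inputs from section 12.0: difference 2.5 s, SD 4 s, 50 per group, two-sided alpha 0.05.

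- Standard error = 4 × √(2/50) = 0.80 s.
- 2.5/0.80 − 1.96 = 1.165, so power is 0.878 (0.872 by noncentral t). This agrees with the stated figure of more than 80%.
- With 55 per group, power is 0.906 by the same formula.
- For 80% power, 41 per group are enough. Losses before the drops therefore have room: 55 to 50 is 5/55 = 9.1%.

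**2. Which reading fits the text?**

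| Step | Where | What it implies |
|---|---|---|
| The anesthesia plan is checked with the attending before the day of surgery and again before randomization | Sections 8.0 and 10.0 | Eligibility is a matter of the plan |
| LMA placed, steady state reached | Section 10.0 | The need for another airway would normally show here, before any drop |
| Drops given, interval timed at administration | Sections 10.0 and 12.0 | The protocol's primary interval is normally recorded before any later airway change |
| Assistance and its duration recorded | Section 10.0 | A response that needs help is data |
| Apnea managed through the LMA | Section 15.0 | The expected response does not meet the section 14.0 example |

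The simplest reading of the example is a child who turns out to need a different airway at placement. For the harmful reading, four things must happen in turn: a response to the drops, failure of support through the LMA, a replacement airway, and deletion of data already recorded. No text supports the last step.

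**3. Size if it happened anyway.** Assumptions not in the documents: each withdrawn child has a change of X = 15 or 20 s, and that child's data are discarded. From the documents: n = 55, povidone-iodine mean 2.5 s, saline mean 0 s.

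- Total povidone-iodine change = 55 × 2.5 = 137.5 s.
- With k povidone-iodine children removed, difference = (137.5 − kX)/(55 − k).
- With one saline child removed, difference = 2.5 + X/54.

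| Removed | X = 15 s | X = 20 s |
|---|---|---|
| None | 2.50 s | 2.50 s |
| One povidone-iodine | 2.27 s | 2.18 s |
| Two povidone-iodine | 2.03 s | 1.84 s |
| One saline | 2.78 s | 2.87 s |

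**4. How far can X be pushed?** With k children at X and all others equal, the smallest possible sample variance is [k(X − m)² + (n − k)(m − m′)²]/(n − 1). Here m is the group mean and m′ the mean of the others.

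- Two povidone-iodine children at 30 s: m′ = (137.5 − 60)/53 = 1.46 s. The variance is at least (2 × 27.5² + 53 × 1.04²)/54 = 29.1, so the SD is at least 5.4 s.
- One saline child at 30 s: the variance is at least (30² + 54 × (30/54)²)/54 = 17.0, so the SD is at least 4.1 s.

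Neither case can occur with the protocol's SD of 4 s. If changes were normal with mean 2.5 s and SD 4 s, a change above 20 s lies (20 − 2.5)/4 = 4.375 SDs out. About 0.0003 such children would be expected among 55.

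**The case for a change.** The strongest case for acting rests on the literal text. There is no cut-off, the example can follow the drops, and the trigger and the outcome are both respiratory. The SAP reports no change in respiration in the saline group, but that covers analyzed children only and cannot show which arm a withdrawn child came from.

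Large responses are also less far-fetched under the protocol's other scenario, SD 8 s with a difference of about 4 s. There 20 s lies (20 − 4)/8 = 2 SDs out, and about 0.0228 × 55 = 1.25 such children would be expected. If withdrawal systematically took the largest povidone-iodine changes and left saline intact (50 per group, SD 4 s, normal changes), losing 5% would give 2.07 s with power 0.77. Losing 10% would give 1.72 s with power 0.62.

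The gap in wording stands, and so does the absence of a defined analysis set. The one-sided loss of 5% or 10% does not stand as evidence. It assumes that the largest responders are removed, in one arm only, and that their intervals are discarded. The documents give no rate for any of this and point the other way on the last step. The SD 8 s scenario makes a large response plausible, but not its removal, since assistance through the LMA is a recorded item.

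How an interval ended by an assisted breath should be timed is a separate question from who is withdrawn, and is not settled here.

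**Conclusion.** The concern identifies a real omission but no error that needs a change to the plan. On its natural reading, section 14.0 removes children whose airway plan changes before the drops. Such losses cannot be caused by the drops. Provided the airway decision does not depend on the allocated solution, they cost numbers only, and the margin of 55 against 50 covers 9.1%.

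A child who responds after the drops stays in, with any assistance recorded. An analyst would sensibly fill the gap by analyzing every randomized child who received drops in the assigned group, keeping the recorded intervals, and accounting for withdrawals by arm in the usual participant flow. The SAP is written in the past tense, so a rewritten withdrawal rule would change nothing in the conduct of the trial.

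If the remote reading had applied to one povidone-iodine child with a change of 15 to 20 s, the difference would fall by 0.23 to 0.32 s from 2.50 s. One saline child would raise it by 0.28 to 0.37 s. These sizes rest on assumed responses and on data being discarded, which neither document states. The actual effect is unknown and may be zero.
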